7.1.2 STANDARD OF CARE STUDY PROCEDURES

Subjects will undergo outpatient therapy at the same regular interval that was established before participation in the trial. Subjects will be prepared for surgery in the usual manner. Preoperative assessments from their primary care provider will be performed with the necessary preoperative assessments. Postoperative care will also be in the same fashion with routine postoperative pain management if necessary. Postoperative follow-up will also be standard at two weeks for a wound check and suture removal, if necessary.

7.2 LABORATORY PROCEDURES/EVALUATIONS

7.2.1 CLINICAL LABORATORY EVALUATIONS

In addition to laboratory evaluations required by the study for preoperative anesthesia assessment, the subject will also undergo a baseline lipid profile.

7.2.2 OTHER ASSAYS OR PROCEDURES

Not Applicable

7.3 STUDY SCHEDULE

7.3.1 SCREENING

Screening Visit

- Obtain informed consent of potential participant verified by signature on written informed consent for screening form.
- Complete or verify completion of HIPAA form for release of PHI

- Review medical history to determine eligibility based on inclusion/exclusion criteria.
- Review medications history to determine eligibility based on inclusion/exclusion criteria.
- Review imaging to determine eligibility based on inclusion/exclusion criteria.
- Perform medical examinations needed to determine eligibility based on inclusion/exclusion criteria.
- Tilt table test to assess for risk of dysautonomia / allocation to autonomic dysfunction group
- Schedule study visits for participants who are eligible and available for the duration of the study.

7.3.2 ENROLLMENT/BASELINE

Enrollment/Baseline Visit (Visit 1, Day 0)

- Obtain informed consent of potential participant verified by signature on study informed consent form.
- Verify inclusion/exclusion criteria.
- Obtain urine pregnancy test.
- Obtain baseline information per the assessment schedule, Table 2
- 24 hour blood pressure monitoring to test for allocation to autonomic dysfunction group
- Record vital signs, results of examinations, and other assessments per the assessment schedule, Table 2
- Complete informed consent process
- Schedule preoperative assessment
- Schedule preanesthesia clinic assessment
- Schedule surgery date

7.3.3 FOLLOW-UP

Surgical Postoperative Visit (10-14 days after surgery)

- Physical examination and inspection of the wounds
- Pain control

Long Follow-up Visits (Month 3, 6, 9, 12, 15 +/- 14 days)

- Record adverse events as reported by participant or observed by investigator.
- Record updates in medications
- Wound check
- Focused Physical Examination for spasticity according the Modified Ashworth Scale
- Vital Signs and tests: blood pressure, temperature, pulse
- Home Training Assessment
- Modified Brain Motor Control Assessment
- Device Electrode Mapping Assessment (Month 3 only)
- Standing Training Assessment
- Other assessments per the assessment schedule, Table 2, aside from Autonomics Assessments
- Record participant's adherence to treatment program.

Short Follow-up Visits (Month , +/- 14 days of monthly visit)

- Record adverse events as reported by participant or observed by investigator.
- Record updates in medications

- Vital Signs and tests: blood pressure, temperature, pulse
- Standing Training Assessment
- Home Training Assessment
- Other assessments per the assessment schedule, Table 2
- Record participant's adherence to treatment program.

7.3.4 AUTONOMICS FOLLOW-UP VISIT

Months 3, 6, and 9 +/- 2 months. Only for subjects in the autonomic dysfunction group.

- Record adverse events as reported by participant or observed by investigator.
- Record updates in medications
- Wound check
- Focused Physical Examination for spasticity according the Modified Ashworth Scale
- Vital Signs and tests: blood pressure, temperature, pulse
- Autonomic Assessments as listed under Modified Procedures

7.3.5 FINAL STUDY VISIT

The final study visit will occur on month 15 of overall involvement in the study. The procedures performed during this visit are as described in Section 7.3.7, Schedule of Events. A 14 day scheduling leeway period is allowed for this visit. In addition to the listed procedures to be performed, adverse events will be recorded as reported by the participant or as observed.

7.3.6 EARLY TERMINATION VISIT

Should the subject be terminated from the study for any reason, their final visit will consist of basic safety screening: a complete physical exam, the Vital Signs and Tests assessment and the Modified Ashworth Scale Assessment if the participant is willing. If the subject's device remains intact, it will be interrogated to check impedances.

7.3.7 UNSCHEDULED VISIT

In the event of an unscheduled patient visit, the subject will undergo safety screening – a focused physical exam, the Modified Ashworth Scale test, and the blood pressure, temperature, and pulse elements of the Vital Signs and Tests assessment. Depending on the reason for the visit, the subject may be referred to the appropriate service for possible adverse event follow up. All adverse events reported by the subject or observed by the investigator will be documented and reported. Aside from adverse events, information gathered at these unscheduled visits will not be included in the statistical analysis.

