5.3 STRATEGIES FOR RECRUITMENT AND RETENTION

Subjects will be recruited via flyer made available at each site through the neurosurgery and PM&R clinics. We anticipate limited enrollment during the first year to establish and test trial infrastructure. Expansion through the additional sites and capacity should double each year until target enrollment. After securing the initial funding source, our clinic receives weekly inquiries about the status of the proposed trial, highlighting the existing potential recruitment network. We anticipate flyers to be widely disseminated throughout this network.

Patients with chronic SCI are highly motivated and very involved in their care. Subjects will be in continuous contact with the study as they complete their home rehabilitation regimen and will be seen on a monthly basis for testing.

Subjects will receive appointment reminders the week prior to their appointments and regular phone calls if their home rehabilitation progress becomes delayed by more than one week.

Subject recruitment will be divided into two phases. In phase 1, 10 subjects will be recruited per protocol. After the recruitment of the 10th subject, recruitment will be temporarily halted. After the 6 month timepoint data collection for these 10 subjects, the safety endpoints and adverse event reports will be submitted to the FDA in a summary format. Recruitment will not continue until FDA review and approval, though additional subjects may be screened and potentially scheduled.

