10.4.4 SAFETY ANALYSES

Safety Endpoints and a summary description are as follows:

- Physical Examination: signs of pressure ulcers, infections, or other relevant emergent findings
- Blood Pressure: change from baseline, before, and after stimulation sessions
- Adverse Event Incidence: as defined by 8.1 Specification of Safety Parameters
- Modified Ashworth Scale Score: changes from baseline, before, and after stimulation settings

Safety endpoints and adverse events will be presented via summary statistics after coding into System Organ Classes (SOCs). As applicable adverse events will only be coded once for each subject. Each adverse event will be described by start date, stop date, severity, relationship, outcome, and duration. AEs will be reported as outlined in 8 ASSESSMENT OF SAFETY.

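### Blood pressure and Ashworth values measured at unscheduled visits are left out of the analysis although Section 10.4.4 names both as safety endpoints; only what is recorded as an adverse event is kept

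*Combined protocol and SAP*

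**What the plan says.** Section 7.3.7 sets the content of an unscheduled visit: "a focused physical exam, the Modified Ashworth Scale test, and the blood pressure, temperature, and pulse elements of the Vital Signs and Tests assessment". It describes this as safety screening. Two sentences then decide what happens to the information. The first protects adverse events: "All adverse events reported by the subject or observed by the investigator will be documented and reported". The second excludes the rest: "Aside from adverse events, information gathered at these unscheduled visits will not be included in the statistical analysis".

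Section 10.4.4 lists four safety endpoints. One is adverse event incidence. The other three are the measures taken at an unscheduled visit:

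- "Physical Examination: signs of pressure ulcers, infections, or other relevant emergent findings"
- "Blood Pressure: change from baseline, before, and after stimulation sessions"
- "Modified Ashworth Scale Score: changes from baseline, before, and after stimulation settings"

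All four are to be presented by summary statistics. The section does not mention unscheduled visits.

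Section 5.3 pauses recruitment after the 10th subject. Once the month 6 data are in, "the safety endpoints and adverse event reports will be submitted to the FDA in a summary format", and recruitment waits for FDA review and approval.

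**The concern.** Sections 7.3.7 and 10.4.4 are not reconciled. One makes the measures compulsory at unscheduled visits and then shuts them out of the analysis. The other treats the same measures as endpoints without saying which visits count. A programmer following 7.3.7 literally would drop the values.

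The omission is unlikely to be neutral. A subject usually comes in between visits because something is troubling them, and 7.3.7 itself foresees referral for possible adverse event follow-up. Dropping values from symptom-prompted visits would tend to leave a set that looks better than everything measured.

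The adverse event exception does not fully close the gap. A coded event is not a change from baseline in mmHg or Ashworth grade, and 10.4.4 lists the two as separate endpoints. Section 8 gives no blood pressure or Ashworth change that must be recorded as an event, so whether a measured worsening survives depends on the investigator's judgement. Section 10.4.4 also codes an event only once per subject where applicable, so a recurrence may not show in the incidence summary.

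At stake are the change-from-baseline safety summaries and possibly the summary on which the restart of recruitment depends.

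**Working it through.** The plan gives no figure on this point to reproduce. The check sets the sections side by side, then asks how often scheduled visits would capture a short episode without help.

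**What 7.3.7 keeps and drops, by endpoint**

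- *Adverse event incidence:* kept in full by 7.3.7.
- *Physical examination:* the endpoint covers emergent findings such as ulcers and infections. Most of these meet the adverse event definition in 8.1.1 and are kept that way. A finding not judged an adverse event is lost.
- *Blood pressure:* hypotension at follow-up is to be entered in the adverse event database (8.1). The measured change from baseline is lost.
- *Modified Ashworth:* a condition that deteriorates is to be recorded as an adverse event (8.3). The measured change from baseline is lost.

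**Scheduled measurements (Table 2 and Section 7.3.3)**

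- Ashworth after implantation: months 3, 6, 9, 12 and 15. Section 7.3.4 adds assessments at months 3, 6 and 9 (+/- 2 months) for the autonomic dysfunction group only.
- Vital signs after implantation: monthly from month 3.
- The postoperative visit at 10–14 days lists examination, wound inspection and pain control, but neither Ashworth nor vital signs.

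At the FDA checkpoint, with 10 subjects and leaving aside the extra autonomic visits:

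- Ashworth: 10 × 2 visits (months 3 and 6) = 20 subject-visits
- Blood pressure: 10 × 4 visits (months 3, 4, 5 and 6) = 40 subject-visits

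**Chance that a scheduled visit falls within an episode**

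For an episode of L days starting at random relative to visits T days apart, P = min(1, L/T). T is 91.3 days for quarterly visits (365.25/4) and 30.4 days for monthly visits (365.25/12). The documents give no episode lengths, so L is an assumption shown over a range.

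| L (days) | Ashworth, L/91.3 | Blood pressure, L/30.4 |
|---|---|---|
| 3 | 3/91.3 = 3% | 3/30.4 = 10% |
| 7 | 7/91.3 = 8% | 7/30.4 = 23% |
| 14 | 14/91.3 = 15% | 14/30.4 = 46% |
| 30 | 30/91.3 = 33% | 30/30.4 = 99% |

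These figures apply from month 3, when the regular schedule starts, and assume that visit dates are not moved because of the episode. They exclude the extra Ashworth assessments in the autonomic group, where the chance is higher.

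The complement of each figure is the chance that scheduled visits miss the episode. It is not the chance that a value is collected and then discarded. That also requires the subject to attend an unscheduled visit during the episode, and the documents give no rate for such visits.

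**The case against.** The strongest reply is that the adverse event route already carries the important information. Section 8.3 requires a deterioration from the screening condition to be recorded as an adverse event and changes in severity to be documented. Section 8.1 names hypotension, surgical site infection and seroma for the adverse event database. Section 10.4.4 reports each event with dates, severity, relationship, outcome and duration, and 7.3.7 keeps all of it. This stands. It means a recognised deterioration should not vanish from the safety results, and it largely answers the point for the examination endpoint. It does not supply the measured changes, and it does not cover a value that nobody judged to be an event.

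A second reply is that the blood pressure and Ashworth endpoints are worded around stimulation sessions or settings, and an unscheduled visit provides no such session. This stands for the before-and-after part. Both endpoints also name change from baseline, which an unscheduled value can supply.

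A reader might go further in three ways that the documents do not support:

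- *That the worst values are removed.* This is plausible, but the documents give neither the reasons for unscheduled visits nor the values found there.
- *That the FDA summary is stripped of these values.* Section 7.3.7 speaks of the statistical analysis, and 5.3 states no data rule for the summary. Adverse event reports go to the FDA in any case.
- *That, since a 14-day episode overlaps a quarterly visit 15% of the time, the other 85% are measured and then dropped.* That assumes every missed episode leads to an unscheduled visit.

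**Conclusion.** The concern holds in a limited form. As written, the rule leaves out measured blood pressure and Ashworth changes from baseline at visits likely to be prompted by a problem, together with any abnormality not judged an adverse event. The likely direction is towards change-from-baseline summaries that look more favourable than what was measured. That direction rests on the assumption that unscheduled visits tend to follow a problem.

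The size cannot be stated, because the rate of unscheduled visits is not given. The overlap figures show only that scheduled visits are a weak substitute for short episodes: 3% to 33% for Ashworth over assumed lengths of 3 to 30 days. For blood pressure the range is 10% to 99%, so the gap there closes for episodes of about a month.

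Whether the FDA summary is affected is open, because the plan does not say. With only 10 subjects at that checkpoint, one subject's omitted worst change concerns 1/10 = 10% of those summarised, so the rule should be settled beforehand. This is a worthwhile, inexpensive correction. It does not invalidate the safety analysis.

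**What to change.** - **Section 7.3.7:** limit the exclusion to efficacy analyses.
- **Section 10.4.4:** keep by-visit summaries on scheduled visits, so that irregular visits do not distort them. Add one table giving, per subject, the worst post-implant change from baseline in blood pressure and in Modified Ashworth, and any emergent examination finding, using scheduled, unscheduled and early termination visits.
- **Section 5.3:** state that the same tables go into the 10-subject FDA summary.

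The measurements are already required, so nothing new is collected and no clinical procedure changes. The cost is a few sentences and one extra table. The drawback is that the safety figures may look slightly less favourable.

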7.3.8 SCHEDULE OF EVENTS TABLE

Table 2

	Screening	Enrollment	Month 3	Month 4	Month 5	Month 6	Month 7	Month 8	Month 9	Month 10	Month 11	Month 12	Month 13	Month 14	Month 15
Procedures															
Spinal Cord Stimulator Implantation		X													
Demographics	X														
General Health History	X														
Epidemiology/Environmental History	X														
History of Disease/Injury Event	X														
Physical Examinations	X	X	X			X			X			X			X
Vital Signs and Other Body Measures															
Vital Signs and Tests	X	X	X	X	X	X	X	X	X	X	X	X	X	X	X
Laboratory Tests	X														
Spinal Imaging / Spinal Cord Imaging	X														
Treatment / Intervention Data															
Assistive/Mobility Devices & Orthosis	X														
Falls Diary	X	X	X	X	X	X	X	X	X	X	X	X	X	X	X
NBSS	X	X	X	X	X	X	X	X	X	X	X	X	X	X	X
NBDS	X					X									X
Rehabilitation Therapies	X														
Surgical and Procedural Interventions	X														
Other Investigational Treatments	X														
Home Training			X	X	X	X	X	X	X	X	X	X	X	X	X
Neurological Outcomes															
Classification of SCI	X														
Modified Ashworth Scale	X		X			X			X			X			X
NINDS Myotatic Reflex Scale	X														
Electrodiagnostics															
Brain Motor Control Assessment	X		X	X	X	X	X	X	X	X	X	X	X	X	X
Device electrode mapping		X	X			X			X			X			X
Standing Training Assessment			X			X			X			X			X
Functional Outcomes	X														
Autonomics															
Autonomic Screening	X														
Autonomic Assessments			a			a			a						
Sympathetic Skin Responses			a						a						
Cognitive			a			a			a						
Pain	X		X			X			X			X			X
Psychological	X		X			X			X			X			X
Quality of Life	X		X			X			X			X			X
Sleep	X		X			X			X			X			X

Items are grouped according to the major categories of 7.1.1 in blue. Categories containing elements administered at different times in the study are expanded and grayed out. 'X' represents mandatory assessments for all subjects. 'a' represents assessments for subjects selected to undergo autonomics protocol.

7.4 JUSTIFICATION FOR SENSITIVE PROCEDURES

Not Applicable.

7.5 CONCOMITANT MEDICATIONS, TREATMENTS, AND PROCEDURES

All concomitant prescription medications taken during study participation will be recorded on the case report forms (CRFs). For this protocol, a prescription medication is defined as a medication that can be prescribed only by a properly authorized/licensed clinician. Medications to be reported in the CRF are concomitant prescription

medications, over-the-counter medications and non-prescription medications. In particular medications that affect the use of muscles and firing of nerves are particularly important including (but not limited to): botulinum toxin injections, muscle relaxants, and antiepileptics.

7.5.1 PRECAUTIONARY MEDICATIONS, TREATMENTS, AND PROCEDURES

In the postoperative phase there is concern for excessive bleeding with blood thinners, anti-platelet agents such as aspirin, or NSAIDs such as ibuprofen. Abstaining from these medications for 30 days after surgery will be discussed with each subject during the preoperative phase.

7.6 PROHIBITED MEDICATIONS, TREATMENTS, AND PROCEDURES

Treatment with botulinum toxin will not be permitted unless discussed with and approved by the study PI or coinvestigator.

7.7 PROPHYLACTIC MEDICATIONS, TREATMENTS, AND PROCEDURES

No prophylactic medications will be administered for this study except local anesthetic and antibiotics during surgery.

7.8 RESCUE MEDICATIONS, TREATMENTS, AND PROCEDURES

There are no known drugs or interventions to be used for rescue.

7.9 PARTICIPANT ACCESS TO STUDY AGENT AT STUDY CLOSURE

The subject will continue to have the epidural stimulator after the completion of the study unless it was removed for safety. The projected duration of battery life for the stimulators is 5 to 10 years on average. Future battery replacements will remain up to the subject.

8 ASSESSMENT OF SAFETY

8.1 SPECIFICATION OF SAFETY PARAMETERS

Safety is not a primary or secondary endpoint of this study but safety is a top concern of the investigators. There is significant experience with epidural spinal cord stimulation amongst the primary and co-investigators for chronic pain and there is significant experience with patients with chronic spinal cord injury. Surgical risk, while low, represents the largest aspect of safety concern for this study. Safety during follow-up testing is also a significant concern as it relates to dysautonomia and falls.

While adverse events will be queried at each appointment and serious adverse events will be monitored and reported, there are specific risk parameters that will be monitored conscientiously during the following time periods:

Perioperative

- Hypotension and hemodynamic instability

- Infection
- Bleeding
- Pain
- Cerebrospinal fluid leak

Follow-up Visits

- Hypotension
- Surgical site infection and seroma

These events will be anticipated and, if found, will be recorded in the adverse event database for review. The Adverse Event Incidence Endpoint will reflect the increased vigilance for these safety outcomes.

8.1.1 DEFINITION OF ADVERSE EVENTS (AE)

Adverse event means any untoward medical occurrence associated with the use of an intervention in humans, whether or not considered intervention-related (21 CFR 312.32 (a)).

8.1.2 DEFINITION OF SERIOUS ADVERSE EVENTS (SAE)

Serious adverse event or serious suspected adverse reaction. An AE or suspected adverse reaction is considered "serious" if, in the view of the investigators, it results in any of the following outcomes: death, a life-threatening adverse event, inpatient hospitalization or prolongation of existing hospitalization, a persistent or significant incapacity or substantial disruption of the ability to conduct normal life functions, or a congenital anomaly/birth defect. Important medical events that may not result in death, be life-threatening, or require hospitalization may be considered serious when, based upon appropriate medical judgment, they may jeopardize the patient or subject and may require medical or surgical intervention to prevent one of the outcomes listed in this definition. Examples of such medical events include significant postoperative epidural hematoma requiring reoperation.

8.1.3 DEFINITION OF UNANTICIPATED PROBLEMS (UP)

Unanticipated problems involving risks to participants or others to include, in general, any incident, experience, or outcome that meets all of the following criteria:

- Unexpected in terms of nature, severity, or frequency given (a) the research procedures that are described in the protocol-related documents, such as the IRB-approved research protocol and informed consent document; and (b) the characteristics of the participant population being studied;
- Related or possibly related to participation in the research ("possibly related" means there is a reasonable possibility that the incident, experience, or outcome may have been caused by the procedures involved in the research); and
- Suggests that the research places participants or others at a greater risk of harm (including physical, psychological, economic, or social harm) than was previously known or recognized.

8.2 CLASSIFICATION OF AN ADVERSE EVENT

8.2.1 SEVERITY OF EVENT

For AEs not included in the protocol defined grading system, the following guidelines will be used to describe severity

- Mild – Events require minimal or no treatment and do not interfere with the participant’s daily activities.
- Moderate – Events result in a low level of inconvenience or concern with the therapeutic measures. Moderate events may cause some interference with functioning.
- Severe – Events interrupt a participant’s usual daily activity and may require systemic drug therapy or other treatment. Severe events are usually potentially life-threatening or incapacitating.

